## 2.5. Randomized intervention

The randomized intervention will be: (1) fenofibrate (or its active metabolite, fenofibric acid) administered for 10 days (see **Appendix 3** for specific preparations and dosing), with appropriate dose reductions or exclusions will be implemented for patients with chronic kidney disease as per the approved preparation label; (2) Placebo of similar appearance (1:1 ratio). These interventions will be added to usual care. Participants and investigators (including research team members who administer the Dyspnea Borg scale and symptoms questionnaires) will be blinded to the randomized intervention. Primary analyses will be performed on an intent-to-treat basis.

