## **2.10. Follow-up assessments**

For participants randomized as inpatients, daily assessments (via medical record review) will be performed to assess clinical status, with particular attention to the study endpoints (death, mechanical ventilation and the  $\text{FiO}_2/\text{SpO}_2$  ratio), until hospital discharge or 30 days (whichever is shortest). For participants discharged prior to 30 days-post randomization, a follow-up call will be performed at the ~30-day time point to assess vital and functional status, symptoms and major adverse events, including hospitalizations.

For participants randomized as outpatients or discharged within 24 hours of receiving the first dose of the study medication, participants will be called at approximately 5, 10, 15 and 30 days post-randomization, in order to assess vital and functional status, hospitalization status, the severity of dyspnea (via the modified Dyspnea Borg Scale, **Appendix 1**) and major adverse events. An effort will be made to make these assessments at the exact time points, but we recognize that this is often not possible due to work schedules and inability to get in touch with participants for various reasons. In these instances, we will make the assessments at time points that are as close as possible to the scheduled time points.

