## 7. STATISTICAL CONSIDERATIONS

### 7.1. Power calculations

We will enroll 700 participants. Participants will be randomized to one of 2 interventions (fenofibrate plus usual care vs. placebo plus usual care). Assuming feasible distributions of participants across each of the five hierarchies from the available published evidence, we performed 10,000 simulations of rank distributions of 700 participants, and determined that there will be 80% power at an alpha of 0.0492 (allowing for one interim analysis at 50% of enrollment with an alpha of 0.0054) to observe an 11% difference in median rank scores between the treatment arms. Power calculations were performed using python and PASS16.

Enrollment of 700 participants will increase our power for secondary outcomes. For the secondary outcome of number of days alive, out of the intensive care unit, free of mechanical ventilation (invasive and non-invasive), extracorporeal membrane oxygenation (ECMO) or maximal available respiratory support in the 30 days following randomization, assuming a standard deviation of 7 (the SD from the REPLACE COVID trial for this outcome), a sample size of 700 would have 90% power to estimate a 1.7 day mean difference between treatment arms. Assuming that the SD may be higher in the current study with the inclusion of outpatients, we would have a sufficient power to estimate a 3.4 day mean difference between treatment arms with a SD of 14.

For the secondary outcome of the WHO ordinal scale, based on the ordinal scale distributions from the Remdesivir trial, we would have 90% power to observe an OR of 1.5 for clinical improvement in the ordinal scale. Given the expected lower severity of illness in our participants, with an adjusted reasonable distribution towards the lower end of the scale, we would have 90% power to observe an OR of 1.7.

For the exploratory outcome of all-cause death, assuming a death rate of 14% (observed in REPLACE COVID), we would have sufficient statistical power to detect a HR of 1.4. Considering the mixed inclusion of inpatients and outpatients, if the death rate is 5%, we would have sufficient statistical power to detect a HR of 1.7.

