### 7.2. Data Analysis Plan

The sample, both the baseline characteristics and the outcomes, will be explored and described using graphical techniques and summary statistics (means, medians, proportions and measures of variability) as appropriate. The initial description will consider the sample as a whole as well as by treatment arm.

The primary outcome variable will be the global rank score, as used previously in several similar randomized controlled trials to facilitate evaluation of composite outcomes of binary and continuous findings accounting for censorship for death. The predictor of interest for all outcomes will be randomized intervention (fenofibrate vs. control), with analyses based upon the total number of randomized participants. Initial descriptive estimates of all measures will be generated for study participants by treatment group. Statistics will include estimates of central tendency, measures of variability, and derived moments of skewness and kurtosis. Analyses of distributional properties will be performed to determine if variance stabilizing or normalizing transformations should be applied. Outliers will be assessed via visual inspection of distributions and checked for accuracy. Additionally, the intervention groups will be compared using Fisher's Exact tests.

The primary and secondary outcomes will be analyzed using a two-sided Wilcoxon rank sum test. Estimation, and 95% confidence intervals, of the differences between arms will be based on the Hodges-Lehman median difference as well as the Mann-Whitney Parameter, the probability that a subject from the fenofibrate arm has a score greater or equal to that of a subject for the control. This will be followed by a more comprehensive linear regression analysis allowing for assessments of the treatment effect on each continuous outcome of interest while controlling for effects of covariates including age, sex, inpatient vs. outpatient status at enrollment,  $\text{FiO}_2/\text{SpO}_2$  at the time of enrollment, ethnicity, body mass index, altitude above sea level and history of diabetes at baseline.

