### Secondary Endpoints (Pre-specified in the protocol)

Secondary endpoints pre-specified in the protocol are:

- (1) Number of days alive, out of the intensive care unit, free of mechanical ventilation (invasive and non-invasive), extracorporeal membrane oxygenation (ECMO) or maximal available respiratory support in the 30 days following randomization.
- (2) A seven-category ordinal scale consisting of the following categories: 1, not hospitalized with resumption of normal activities; 2, not hospitalized, but unable to resume normal activities; 3, hospitalized, not requiring supplemental oxygen; 4, hospitalized, requiring supplemental oxygen; 5, hospitalized, requiring nasal high-flow oxygen therapy, noninvasive mechanical ventilation, or both; 6, hospitalized, requiring extracorporeal membrane oxygenation (ECMO), invasive mechanical ventilation, or both; and 7, death.
- (3) A global rank score similar to the primary endpoint, but using a more comprehensive COVID-19 symptom scale instead of the dyspnea Borg scale (Appendix 1 of Protocol).

**Exploratory endpoints** will include:

- (1) Time to all-cause death.
- (2) Time to hospitalization among subjects initially randomized as outpatients
- (3) Time to discharge among subjects initially randomized as inpatients
- (4) Number of days alive and out of the hospital during the 30 days following randomization.
- (5) A global rank score similar to the primary endpoint, but built only with factors 1-4

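### The ordinal-scale power statement overstates power at OR 1.50 (at most about 86.5% with 700, not 90%), and neither the category distribution nor the assessment day behind it is given

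*Protocol*

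**What the plan says.** Protocol section 7.1 opens with "We will enroll 700 participants". For the ordinal scale it then works "based on the ordinal scale distributions from the Remdesivir trial" and concludes that "we would have 90% power to observe an OR of 1.5 for clinical improvement in the ordinal scale". The next sentence turns to the milder illness expected in this trial and says that "with an adjusted reasonable distribution towards the lower end of the scale, we would have 90% power to observe an OR of 1.7". The method cited is the standard sample-size formula for ordered categorical data (Protocol reference 27). Neither sentence gives category proportions, a study day or an alpha.

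On the test, Protocol section 7.2 states: "The primary and secondary outcomes will be analyzed using a two-sided Wilcoxon rank sum test". The SAP keeps the Wilcoxon test for continuous secondary outcomes and names none for this scale.

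The scale is defined in the Protocol summary, Protocol section 3 and the SAP. The SAP wording begins "A seven-category ordinal scale consisting of the following categories: 1, not hospitalized with resumption of normal activities". None of the three definitions says when the scale is read, or whether it is a status on one day or a worst status. The secondary endpoint listed just before it does have a window, the 30 days after randomization.

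On contacts, Protocol section 2.10 and Appendix 2 provide daily record review for inpatients while admitted. After that, "For participants discharged prior to 30 days-post randomization, a follow-up call will be performed at the ~30-day time point". Outpatients, and inpatients discharged within 24 hours of the first dose, are called at about days 5, 10, 15 and 30.

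**The concern.** The cited formula puts a ceiling on power that does not depend on the missing distribution, because with seven categories an even split is the most favourable case. If the ceiling lies below 90% at OR 1.50, the statement fails at its printed value and no outside source is needed to show it.

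The OR 1.7 statement does depend on the distribution, and the distribution depends on the day. The more participants sit in one category, the less an ordinal comparison can detect. With no day and no proportions, a reader cannot tell whether 90% at OR 1.7 is realistic. What is at stake is how a null result on this secondary endpoint would be interpreted.

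**Working it through.** **Inputs.** N = 700 (section 7.1), 1:1 allocation (section 2.5), so 350 per arm. OR 1.5 and 1.7, each with 90% power (section 7.1). Two-sided test (section 7.2). Alpha is not stated for this endpoint; 0.05 is assumed. The category proportions p (averaged over arms) are not in the documents and are treated as unknown.

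**Which convention does section 7.1 use?** The neighbouring figures can be reproduced. For a mean difference, the detectable value at 90% power and two-sided 5% is SD × √(2/350) × (1.960 + 1.2816):
- SD 7: 1.715, printed as 1.7
- SD 14: 3.43, printed as 3.4
- SD 8: 1.96, printed as 2
- SD 16: 3.92, printed as 3.9

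So the section works two-sided at 5% and rounds to at most one decimal.

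**Ordinal-scale formula.**
- N = 12(z_α/2 + z_β)² / [(ln OR)² (1 − Σp³)]
- power = Φ( ln OR × √(N(1 − Σp³)/12) − z_α/2 )

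**OR 1.50, best case.** (1.960 + 1.2816)² = 10.507 and (ln 1.5)² = 0.1644, so 12 × 10.507 / 0.1644 = 767 before division by (1 − Σp³), which is below 1. Seven equal categories give the smallest possible Σp³, 7 × (1/7)³ = 0.0204, so 1 − Σp³ = 0.9796.
- N for 90% power: 767 / 0.9796 = 783.
- Power at 700: Φ(0.4055 × √(700 × 0.9796/12) − 1.960) = Φ(1.105) = 86.5%. Simulating the tie-corrected Wilcoxon test (100,000 runs) gives 86.3%.
- Smallest OR with 90% power: exp √(126.09 / (700 × 0.9796)) = 1.535.
- With alpha 0.0492, the final alpha of the primary endpoint, power is 86.4%. A one-sided 5% test would give 92.2%, but section 7.2 specifies two-sided and the neighbouring figures fit two-sided.

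**When would the detectable OR print as 1.5?** It must be below 1.55, which requires Σp³ ≤ 1 − 126.09 / (700 × (ln 1.55)²) = 0.062. A split of 35/15/15/10/10/10/5% qualifies (Σp³ = 0.053, detectable OR 1.547). As a rough guide, no category can exceed about 35%, with the rest well spread.

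**OR 1.7.** 90% power requires Σp³ ≤ 1 − 126.09 / (700 × 0.2816) = 0.36.

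**Illustrations.** The shares are assumptions, with the remainder spread evenly over the other six categories.

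| Largest category | Σp³ | Power at OR 1.50 | OR with 90% power | Power at OR 1.70 |
|---|---|---|---|---|
| 50% | 0.128 | 82% | 1.58 | 97% |
| 60% | 0.218 | 78% | 1.62 | 95% |
| 70% | 0.344 | 71% | 1.69 | 91% |
| 80% | 0.512 | 58% | 1.84 | 81% |

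The cube root of 0.36 is 0.71, so no category above 71% is necessary for 90% at OR 1.7. It is not sufficient: a 71/29 split has Σp³ = 0.382 and power 89.0%.

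**Assessment day.** Categories 1 and 2 differ only in whether normal activities have resumed, which requires contact with the participant. Inpatients discharged more than 24 hours after the first dose have no call before about day 30. The ~30-day contact is therefore the only single time point at which all seven categories can be scored for everyone.

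**The case against.** The strongest reply is printed precision. Section 7.1 visibly rounds its detectable effects, and a detectable OR of 1.535 to 1.549 would print as 1.5. This stands in part: a reader might infer that 90% power is out of reach on any day and that the printed figure is a plain arithmetic error, and the documents do not support that. The figure could be a rounded 1.54 or 1.55 from a nearly even distribution. Whether the cited trial's distribution was that even cannot be checked from the documents. Rounding does not rescue 90% at 1.50 itself.

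Second, OR 1.5 is the reference scenario. The protocol itself moves to OR 1.7 for the population it expects, and that is attainable. This also stands, so it would be wrong to infer that the design lacks 90% power at the OR meant for this trial. By the same rounding, a detectable OR just below 1.75 would print as 1.7, which relaxes the limit on Σp³ to about 0.42. An 80% share would still miss it.

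Third, shares of 70% or 80% in one category appear nowhere in the documents. That is right, and they serve only as illustrations.

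Finally, a reader might infer that the schedule supports no day but day 30. That is too broad. Inpatients have daily data while admitted, outpatients are called four times, and an earlier reading loses only the split between categories 1 and 2, for inpatients already discharged. A worst-status summary would also be possible.

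**Conclusion.** The point holds in a limited form. At OR 1.50 the stated 90% is not delivered under any category distribution: the ceiling is about 86.5%, a gap of 3.5 percentage points at best, and 90% would take at least 783 participants. This rests on the cited formula, two-sided 5% and all 700 participants analysed. The 90% attached to OR 1.7 is neither confirmed nor refuted. It holds if Σp³ is at most about 0.36, and the documents give neither the distribution nor the day needed to judge that.

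The missing assessment day is real in both documents. On its own it is mostly a missing detail; it matters here because the power figure depends on it. This is a secondary endpoint, so neither the primary analysis nor the choice of 700 is called into question.

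**What to change.** In Protocol section 7.1:
- State the alpha and show the assumed category distribution.
- Restate the first figure as the detectable OR to two decimals (no lower than 1.54 with 700), or as at most about 86% power at OR 1.50.
- Make the OR 1.7 statement conditional on Σp³ of at most 0.36, rather than on a limit for the largest category alone.

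In Protocol section 3 and the SAP, name the day to which that distribution applies. In the current schedule the ~30-day contact is the only single time point that separates categories 1 and 2 for all participants. If the sponsor prefers another day or a summary such as worst status, the text should say how discharged inpatients are scored. The SAP should also name the test for this scale.

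The cost is wording only, with no added visits, participants or data. The one downside is a slightly less favourable stated figure.

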For the exploratory outcome of number of days alive and out of the hospital, assuming a standard deviation of 8 (the SD from the REPLACE COVID trial for this unpublished outcome), a sample size of 700 would have 90% power to estimate a 2 day mean difference between treatment arms. Assuming that the SD may be higher in the current study with the inclusion of outpatients, we would have a sufficient power to estimate a 3.9 day mean difference between treatment arms with a SD of 16.

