### Secondary Analysis:

**Time-to-event outcomes.** Kaplan-Meier curves and cumulative event plots will be used to graphically explore differences between arms. The Cox model will be used to assess differences by arm in the risk of all-cause death and the risk of hospitalization for subjects who were outpatient at the time of randomization. Subjects who withdrew from the study will be considered censored. The proportional hazards assumption will be assessed, and violations addressed using a time by intervention term or a parametric model. Time to discharge from hospital will be modelled using a competing risk model with death as the competing risk.

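### Section 7.1 claims sufficient power for all-cause death at HR 1.4 and HR 1.7, but 700 participants give about 38% and 35%

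*Protocol*

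**What the plan says.** Protocol section 7.1 fixes the sample size ("We will enroll 700 participants"), and section 2.5 gives 1:1 allocation. For the exploratory outcome of all-cause death, section 7.1 considers two mortality levels:

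- At 14%, the rate seen in an earlier COVID-19 trial: "we would have sufficient statistical power to detect a HR of 1.4".
- For the mixed inpatient and outpatient population: "if the death rate is 5%, we would have sufficient statistical power to detect a HR of 1.7".

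Neither sentence gives a power value, an alpha, a number of deaths, or the arm to which the rate applies. The references attached are two Cox sample-size papers, one of them Schoenfeld's.

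The section uses the same term for two mean differences: "we would have a sufficient power to estimate a 3.4 day mean difference between treatment arms with a SD of 14" and, for days alive and out of the hospital, "we would have a sufficient power to estimate a 3.9 day mean difference between treatment arms with a SD of 16". Where it does give a number, power is 80% for the primary endpoint and 90% for the other outcomes.

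Protocol section 7.2 assigns death to a Cox model, and the SAP keeps this: "The Cox model will be used to assess differences by arm in the risk of all-cause death". The SAP gives no power calculation.

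**The concern.** The precision of a hazard ratio depends on the number of deaths. At the stated rates the trial would see about 98 or 35 deaths, which is few for hazard ratios as modest as 1.4 and 1.7.

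If the claim is wrong, section 7.1 credits the trial with a sensitivity for mortality that it lacks. A reader who relies on it could take a non-significant Cox result as evidence against a HR of 1.4 or 1.7. Death is also the top tier of the primary ranking, so readers will look closely at the mortality result even though it is exploratory as a separate endpoint.

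**Working it through.** **Inputs.** From the protocol: N = 700, 1:1 allocation (350 per arm), mortality 14% or 5%, HR 1.4 or 1.7, Cox model. Assumed because not stated for death: two-sided alpha 0.05, and the quoted rates as overall rates. No allowance is made for missing data (under 5% is expected), which could only lower power.

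**Deaths.** 700 × 0.14 = 98 and 700 × 0.05 = 35.

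**Power (Schoenfeld).** Power = Φ(|ln HR| × √(0.25 D) − 1.96), where D is the number of deaths.

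- HR 1.4, D = 98: 0.3365 × √24.5 = 1.665; Φ(1.665 − 1.96) = **38.4%**.
- HR 1.7, D = 35: 0.5306 × √8.75 = 1.570; Φ(1.570 − 1.96) = **34.8%**.

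The formula uses |ln HR|, so the reciprocal HRs (0.71 and 0.59) give the same power for the same number of deaths.

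**Other readings.**

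| Reading | HR 1.4, 14% | HR 1.7, 5% |
|---|---|---|
| Two-sided 0.05, overall rate | 38.4% | 34.8% |
| Alpha 0.0492 | 38.2% | 34.6% |
| Freedman formula | 37.8% | 33.5% |
| Simulated log-rank test, 20,000 runs | 38.1% | 33.5% |
| Rate is placebo-arm rate, HR harmful | 44.0% (115.6 deaths) | 44.2% (46.7 deaths) |
| Rate is placebo-arm rate, HR protective | 34.0% (84.7 deaths) | 28.8% (27.9 deaths) |
| One-sided 5% | 50.8% | 47.0% |
| 700 per arm (contradicts the protocol) | 65.4% | 60.3% |

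None reaches 80%.

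**What the section's other uses of the term amount to.** For a mean difference d, power = Φ(d / (SD × √(2/350)) − 1.96).

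- 3.4 days, SD 14: 3.4/1.058 = 3.213; power 89.5%.
- 3.9 days, SD 16: 3.9/1.209 = 3.224; power 89.7%.

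The two mean differences stated with 90% power also reproduce: 1.7 days with SD 7 gives 89.5%, and 2 days with SD 8 gives 91.1%.

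**Detectable HR with 700 participants.** HR = exp((1.96 + z) × 2/√D), with z = 0.8416 for 80% power and 1.2816 for 90%.

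| Deaths | 80% power | 90% power |
|---|---|---|
| 98 | 1.76 (0.57) | 1.92 (0.52) |
| 35 | 2.58 (0.39) | 2.99 (0.33) |

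**Deaths needed for the stated HRs at 80% power.** D = 4 × 2.8016² / (ln HR)².

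- HR 1.4: 277.3, so 278 deaths, or 278/0.14 ≈ 1,986 participants. With 700 participants, mortality would have to be 277.3/700 = 39.6%.
- HR 1.7: 111.5, so 112 deaths, or 112/0.05 = 2,240 participants. With 700 participants, mortality would have to be 111.5/700 = 15.9%.

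**Precision of a null result.** At an observed HR of exactly 1.0 the 95% limits are exp(±3.92/√D): 0.67 to 1.49 with 98 deaths and 0.52 to 1.94 with 35. Neither interval excludes the HR claimed for that scenario.

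**A possible source.** A 1:1 treatment indicator has variance 0.25. If a variance of 1 is entered instead, the HR detectable with 90% power is exp(3.2415/√D) = 1.39 with 98 deaths and 1.73 with 35, close to the stated 1.4 and 1.7. One of the two cited papers concerns nonbinary covariates, which fits. The documents do not show the software inputs, so this remains a conjecture, and the finding does not depend on it.

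**The case against.** The strongest objection is that the protocol makes no numeric claim for death. The word sufficient is never defined, alpha and sidedness are not given, and 14% and 5% are not identified as overall or placebo-arm rates. The benchmark of about 90% is inferred from two neighbouring sentences. This is fair as to wording: 90% is not a declared standard for mortality. It does not rescue the claim, because every reading above stays below 80%, the lowest power figure the section itself uses.

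The second objection is that little depends on the error. Death is exploratory, the sample size rests on simulation of the global rank score, and no stopping bound or success criterion in the documents uses these HRs. That stands, and it limits the consequence to interpretation of the mortality result.

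The third is that the SAP contains no power section, so its silence is not a second error. That also stands. The SAP matters here only because it keeps the Cox comparison to which the claim refers.

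**Conclusion.** The claim in section 7.1 is wrong as written. Power for death is about 38% at HR 1.4 with 14% mortality and about 35% at HR 1.7 with 5% mortality. A true effect of the stated size would be missed in about 62% or 65% of trials. These figures assume a two-sided alpha of 0.05 and overall mortality rates. Taking the rates as placebo-arm rates gives 34% to 44% and 29% to 44%, and the conclusion is unchanged. It should be fixed because it invites over-reading of a null mortality result. The sample size and the primary analysis are unaffected.

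**What to change.** Replace the two death sentences in section 7.1 with text such as:

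> For the exploratory outcome of all-cause death, with two-sided alpha 0.05 and overall mortality of 14% (98 deaths), 700 participants give 80% power for a HR of about 1.76 (0.57) and 90% power for about 1.92 (0.52). With 5% mortality (35 deaths) the corresponding HRs are about 2.58 (0.39) and 2.99 (0.33). The trial is not powered for mortality; the HR will be reported with its 95% CI.

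Giving both power levels keeps the statement comparable with the 80% and 90% figures in the rest of the section. If the protocol is no longer open to amendment, the same text can go in the SAP or the trial report.

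A minor correction can be made at the same time. The SD of 16 assumed for days alive and out of the hospital exceeds 15, the largest SD possible on a 0 to 30 day scale (half the values at each end). At SD 15 the difference detectable with 90% power is 3.2415 × 15 × √(2/350) = 3.68 days, so the stated 3.9 days errs on the cautious side.

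The cost is wording only: no extra patients and no change to the sample size or to any analysis. The stated sensitivity for mortality becomes less favourable.
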